Note the gatekeeping strategy only allows formal hypothesis testing of 1.5 mg HS or 1.5 mg BID if the higher doses meet statistical significance. Given prior studies with histologic endpoints, there is a strong rationale suggesting that higher doses will have a greater benefit on the primary efficacy endpoint of

Adare Pharmaceuticals SP-1011-002

APT-1011

histology.

Efficacy analysis for Part 2

Sustained EoE response will be assessed in subjects who complete both Part 1 and Part 2 and complete Week-26 and 52 evaluations. This will be assessed by the primary endpoint.

Other measures of efficacy will be assessed at Week 26.

Efficacy will be summarized for histologic non-responders from Part 1 who are treated in Part 2.

Other measures of efficacy will be assessed at Week 52.

The primary focus of Part 2 will be descriptive in nature.

Secondary and exploratory efficacy analysis

Formal statistical hypothesis testing will be used to evaluate treatment benefit with respect to the reduction in number of dysphagia episodes. For each dose that meets the criterion for statistical significance on the primary efficacy outcome, a Wilcoxon Rank-Sum test will be used to test whether the reduction in the number of dysphagia episodes from baseline is larger for the treatment group compared to the control. The hypothesis to be tested is:

 $H_0: R_{1i}(x) \le R_{0i}(x)$ 

 $H_1: R_{1i}(x) > R_{0i}(x)$ 

Where  $R_{ij}(x)$  is the distribution function for the reduction in number of dysphagia episodes for treatment group i (=0 for control, 1 for treatment) and dose j. Holm's step-down procedure will be used to control the overall Type I error at 0.05, where the number of doses considered for inferential testing is equal to the number of doses that meet statistical significance for the primary efficacy analysis.

Statistical tests to compare each APT-1011 dosing group with placebo will be performed for other secondary efficacy endpoints, but the corresponding p-values will be considered as descriptive rather than inferential. The secondary endpoints will be analyzed via a stratified Cochran-Mantel-Haenzel test for categorical endpoints and analysis of covariance or Wilcoxon Rank-Sum tests for change from baseline endpoints, except for the endpoint of time to relapse after initiation of double-blind treatment in Part 2, which will be analyzed using Kaplan-Meier methods.

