#### 8.8.3 Secondary and Exploratory Efficacy Analysis

Statistical tests to compare each APT-1011 dosing group with placebo will be performed for the secondary efficacy endpoints, but the corresponding p-values will be considered as descriptive rather than inferential. The secondary endpoints will be analyzed via a Cochran-Mantel-Haenzel test for categorical endpoints and analysis of covariance for change from baseline endpoints, except for the endpoint of time to relapse after initiation of double-blind treatment in Part 2, which will be analyzed using Kaplan-Meier methods.

As a secondary efficacy analysis, all 4 doses of active treatment will be pooled and compared to placebo with a one-sided test of two proportions.

Additionally,

a logistic regression model using both dose and frequency and dose-frequency interaction will be used to analyze the primary endpoint. Formal statistical hypothesis testing will be used to

Adare Pharmaceuticals SP-1011-002 APT-1011

evaluate treatment benefit with respect to the reduction in number of dysphagia episodes. For each dose that meets the criterion for statistical significance on the primary efficacy outcome, a Wilcoxon Rank-Sum test will be used to test whether the reduction in the number of dysphagia episodes from baseline is larger for the treatment group compared to the control. The hypothesis to be tested is:

 $H_0: R_{1i}(x) \leq R_{0i}(x)$ 

 $H_1: R_{1j}(x) > R_{0j}(x)$ 

Where  $R_{ij}(x)$  is the distribution function for the reduction in number of dysphagia episodes for treatment group i (=0 for control, 1 for treatment) and dose j. Holm's step-down procedure will be used to control the overall Type I error at 0.05, where the number of doses considered for inferential testing is equal to the number of doses that meet statistical significance for the primary efficacy analysis.

Statistical tests to compare each APT-1011 dosing group with placebo will be performed for other secondary efficacy endpoints, but the corresponding p-values will be considered as descriptive rather than inferential. The secondary endpoints will be analyzed via a stratified Cochran-Mantel-Haenzel test for categorical endpoints and analysis of covariance or Wilcoxon Rank-Sum tests for change from baseline endpoints, except for the endpoint of time to relapse after initiation of double-blind treatment in Part 2, which will be analyzed using Kaplan-Meier methods.

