6.6. STATISTICAL TESTS

The default significant level will be 5%; confidence intervals will be 90% and all tests will be one-sided.

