6.7. COMMON CALCULATIONS

For quantitative measurements, change from baseline will be calculated as:

Test Value at Visit X – Baseline Value

For certain parameters percentage change from baseline will be calculated as

• 100 x (Test Value at Visit X – Baseline Value)/Baseline Value

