Copyright © 2009, 2010, 2012, 2016, 2018 IQVIA. All rights reserved. The contents of this document are confidential and proprietary to IQVIA Holdings Inc. and its subsidiaries. Unauthorized use, disclosure or reproduction is strictly proh bited.

Page 45 of 70

percentages.

No statistical testing will be performed.

16.2.3.4. Analysis of Change from baseline in each of Global EoE Symptom Score, Total EREFs Score, Number of Dysphagia Episodes, 7-day EEsAI total score, 7-day EEsAI VDQ and AMS subscores The change from baseline in each of Global EoE Symptom Score (see section 16.2.1.4), 7-day EEsAI total score (see section 16.2.1.6) and 7-day EEsAI VDQ and AMS subscores (see section 16.2.1.7) will be summarized as continuous variables, and analysis of covariance (ANCOVA) will be used to compare the mean change from baseline in each of the APT-1011 dosing groups to placebo, at the Week 12 visit, with the estimated mean difference, 90% confidence interval of the mean difference and 1-sided p-values provided. This statistical testing at Week 12 is considered descriptive only and no adjustments will be made for multiple comparisons. The ANCOVA models will include the factors described in section 7.1.

All these change from baseline analyses will only include data while subjects are receiving double-blind study drug. Data will not be not included for visits after a histologic non-responder at Week 12 had received single-blind (to subject) APT-1011 3 mg BID in Part 2.

For the analysis of change from baseline in the number of dysphagia episodes (see section 16.2.1.5) and dysphagia free days, for each dose that meets the criterion for statistical significance on the primary efficacy outcome, a Wilcoxon Rank-Sum test will be used to test whether the reduction in the number of dysphagia episodes from baseline is larger for the APT-1011 dosing group compared to the control.

Holm's step-down procedure (Holm, 1979) will be used to control the overall Type I error at 0.05, where the number of doses considered for inferential testing is equal to the number of doses that meet statistical significance for the primary efficacy analysis.

Holm's step down procedure will be implemented as follows:

Let the number of APT-1011 doses that meet statistical significance in the primary efficacy analysis be represented by d (where d is between 1 and 4 inclusive for this study).

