Perform the Wilcoxon-Rank Sum test for each of the d doses vs placebo and rank the resulting p-values in ascending order: $p_1 \le p_i \le p_d$

Author: Version Number: 3.0

Version Date: 06NOV2019

Template No.: CS_TP_BS016 Revision 5 Reference: CS_WI_BS005

Page 46 of 70

For each dose the hypothesis to be tested is:

 H_0 : $Ri(x) \leq R_0(x)$

H1: $Ri(x)>R_0(x)$

where $R_i(x)$ and $R_0(x)$ are the distribution functions for the reduction in number of dysphagia episodes for APT- 1011 dosing group i and placebo respectively.

Step 1: Test the dose with smallest p-value (p₁)

The hypothesis H_0 will be rejected if the one-sided p-value p_1 is $\leq 0.05/d$

Step 2: Test the dose with second smallest p-value (p₂)

The hypothesis H_0 will be rejected if the one-sided p-value p_2 is < 0.05/d-1

Step 3: Test the dose with third smallest p-value (p₃)

The hypothesis H_0 will be rejected if the one-sided p-value p_3 is < 0.05/d-2

Step 4: Test the dose with fourth smallest p-value (p₄)

The hypothesis H_0 will be rejected if the one-sided p-value p_4 is < 0.05/d-3

Note that depending on the value of d, not all of these steps may be required.

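### The formal dysphagia hypotheses are printed with the inequality reversed in both documents, contradicting the wording and power calculation that accompany them; the tail of this one-sided test needs to be pinned down

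*SAP*

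**What the plan says.** SAP 16.2.3.4 compares each dose that succeeds on the primary endpoint with placebo by a Wilcoxon rank-sum test, under Holm at an overall 0.05. In words, the aim is to "test whether the reduction in the number of dysphagia episodes from baseline is larger for the APT-1011 dosing group" than for control. The formal pair that follows is H0: R_i(x) ≤ R_0(x) and H1: R_i(x) > R_0(x), where the R's "are the distribution functions for the reduction in number of dysphagia episodes" for dose i and for placebo.

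The protocol does the same twice. The synopsis (Statistical methodology) defines that R "is the distribution function for the reduction in number of dysphagia episodes for treatment group i", and Protocol 8.8.3 repeats the definition and the inequality. Protocol 8.8.3 also gives the aim in words: to see whether the reduction in "episodes from baseline is larger for the treatment group compared to the control".

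Three other provisions bear on the point:

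- SAP 6.6 states that "confidence intervals will be 90% and all tests will be one-sided".
- SAP 6.7 defines change from baseline as "Test Value at Visit X – Baseline Value".
- SAP 7.4 puts only dysphagia episodes, among the secondary endpoints, under multiplicity control.

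SAP 16.2.3.4 names dysphagia-free days in the same sentence as episodes but gives no direction for them. Neither document names strata for this test. The primary CMH test (SAP 16.1.3) uses both randomization factors, and the Bayesian model that covers dysphagia (SAP 16.1.5) includes them.

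**The concern.** If R is a distribution function in the usual sense, R(x) is the probability that a subject's reduction is at most x. A treatment that produces larger reductions has a lower R(x). The printed H1 therefore describes harm relative to placebo, and benefit falls inside the printed H0.

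In a two-sided test this would be cosmetic. Here the one-sided p-value is the decision rule, and a p-value of 0.01 in one tail is 0.99 in the other. A programmer who follows the sentence tests for benefit; one who follows the formula tests for harm. No line in either document says which tail supplies the p-value.

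The point is live. Protocol 2.5 reports that the primary endpoint was met at all four doses, so all four enter the Holm procedure, and SAP version 3.0 still carries the reversed inequality.

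**Working it through.** **1. Direction of the inequality.** Inputs: SDs of 4.5 (placebo) and 7.5 (active) and a difference of 5.0 from Protocol 8.1.1. A placebo mean reduction of 7.5 is assumed, the midpoint of the 5 to 10 expected there, so the active mean is 12.5. With R(x) = Φ((x − mean)/SD):

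| x | placebo R(x) | active R(x) |
|---|---|---|
| 5 | Φ(−0.56) = 0.289 | Φ(−1.00) = 0.159 |
| 10 | Φ(0.56) = 0.711 | Φ(−0.33) = 0.369 |
| 15 | Φ(1.67) = 0.952 | Φ(0.33) = 0.631 |

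Benefit gives R_active < R_placebo, the opposite of the printed H1. Because the SDs differ, the two curves cross where (x − 7.5)/4.5 = (x − 12.5)/7.5, that is at x = 0. Only 4.8% of each arm lies below that point.

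**2. The plan's own power.** The standard error is √(4.5²/20 + 7.5²/20) = √3.825 = 1.956, and 5.0/1.956 = 2.556. One-sided at 0.05:

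- normal approximation: Φ(2.556 − 1.645) = 0.819
- noncentral t: 0.807 (38 df) or 0.804 (Satterthwaite)

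For 6.3 episodes at 0.05/4 = 0.0125, the noncentral t gives 0.809 or 0.802. The stated 80% is reproduced in both cases, for a larger reduction on active treatment. Two-sided versions give only about 0.70 to 0.72 for 5.0 episodes.

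**3. Both tails of the Wilcoxon test.** In 20,000 simulated trials with normal reductions, 20 per arm and one-sided 0.05:

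- intended tail (larger reduction on APT-1011): rejects in 78%
- printed tail: 0 rejections

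A normal approximation agrees for the printed tail: Φ(−2.556 − 1.645) = Φ(−4.20), about 0.00001. With 6.3 episodes at 0.0125, the rates are again 78% and 0.

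**4. Strata.** The documents give no stratum effect, so a range is assumed: four equal strata (5 per arm in each), each factor shifting the reduction by b episodes, SDs of 4.5 and 7.5 within strata, 6,000 trials per setting, one-sided 0.05.

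| b | Wilcoxon power | van Elteren power | Wilcoxon type I | van Elteren type I |
|---|---|---|---|---|
| 0 | 0.79 | 0.77 | 0.058 | 0.057 |
| 2 | 0.78 | 0.77 | 0.055 | 0.060 |
| 4 | 0.73 | 0.76 | 0.038 | 0.056 |
| 6 | 0.67 | 0.78 | 0.025 | 0.056 |

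Ignoring the strata does not raise the error rate above that of the stratified test. It costs power only when the strata are strongly prognostic.

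**5. Baseline count.** Assume reductions of 25% (placebo) and 45% (active), the midpoints of the ranges in Protocol 8.1.1. The difference is then 0.20 × 25 = 5.0 at a baseline mean of 25. Power for plain Wilcoxon against rank ANCOVA on the baseline count, by assumed baseline SD:

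- SD 1.7: about 0.79 for both
- SD 5: 0.785 v 0.805
- SD 8: 0.774 v 0.838
- SD 10: 0.767 v 0.868

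Protocol 8.1.1 expects most controls to have 25 to 35 episodes per week. With a normal distribution centred at 30, an SD of 8 puts 47% in that range and an SD of 10 puts 38%. The larger gains therefore fit the protocol's expectation poorly.

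**The case against.** The strongest reply is that the intended direction is clear. Both documents say in words that the test looks for a larger reduction on active treatment, and the planned power reproduces only in that direction. A sensible programmer would use the sentence. This stands. A reader might infer from the formula that the trial's test is specified backwards and can succeed only if APT-1011 does worse than placebo; the documents taken as a whole do not support that. What remains is that the formal statement says the reverse, three times, in a one-sided setting with no tail named. The repetition makes a text-extraction fault unlikely, and neither document defines R as one minus the distribution function, which would make the inequality correct.

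A reader might also see a second sign error in SAP 6.7. It is not one: that is a general convention for change, while the dysphagia test is defined on a reduction, which Protocol 8.1.1 treats as positive. Nor is dysphagia-free days given a wrong direction, because the rule about a larger reduction is written only for episodes. The direction for free days is simply unstated.

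It could be said that the p-values are only descriptive, as the opening of SAP 16.2.3 puts it for secondary endpoints. SAP 7.4 and the Holm steps in 16.2.3.4 treat dysphagia episodes as the exception.

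Finally, it would be tempting to call the unstratified test an error, or to say that it gives away power for nothing. The test is prespecified and valid, and stratifying loses about 2 points of power if the strata are not prognostic.

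**Conclusion.** The printed hypotheses are reversed relative to the stated aim and to the power calculation, and should be corrected. At the protocol's planning values, choosing the tail by the formula instead of the words takes power from about 78% to about 0% on the only multiplicity-controlled secondary endpoint. These figures rest on normal reductions with the protocol's SDs and on the standard meaning of a distribution function. Whether any analysis used the wrong tail cannot be told from the documents.

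The omission of the strata and the baseline count is a matter of efficiency. Its size depends on stratum effects and a baseline SD that the documents do not give. Adjusting for the baseline count gains about 0 to 2 points at baseline SDs of 1.7 to 5, and more only at larger SDs.

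**What to change.** 1. In the protocol synopsis, Protocol 8.8.3 and SAP 16.2.3.4, reverse **both** lines: H0: R_i(x) ≥ R_0(x) for all x, against H1: R_i(x) ≤ R_0(x), strict for some x. Changing H1 alone would leave it inside the existing H0. Alternatively, keep the inequalities and define R as one minus the distribution function. Because the planning curves cross at zero, it would help to add that the test targets a probability above 1/2 that a reduction on APT-1011 exceeds one on placebo; at the planning values this is Φ(5/√76.5) = 0.72.
2. Define the reduction in episodes as baseline minus visit, and improvement in dysphagia-free days as visit minus baseline. Name the tail that gives the one-sided p-value for each.
3. Confirm and record which tail was programmed.
4. As a cheap improvement, add a van Elteren test, or a rank ANCOVA with the two strata and the baseline 14-day count, labelled as a sensitivity analysis. It should not replace the planned Wilcoxon test: Protocol 2.5 shows that Week 12 results are known, and SAP 4.2 makes that analysis final for Week 12 endpoints. With about 20 subjects per arm over four strata, cells will be small.

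Items 1 to 3 restore the direction already given in words. They cost a few lines of text and one code check, and Holm is unchanged. Item 4 costs one further procedure call.

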16.2.3.5. Analysis of PGIC

The number and percentage of subjects in each PGIC category (see section 16.2.1.10) will be presented for each of the randomized dosing groups at each post-baseline visit. Data will not be included for visits once a subject has switched to single-blind (to subject) APT-1011 3 mg BID.

No statistical testing will be performed.

16.2.3.6. Analysis of percentage of histologic non-responders at Week 12, Week 26, and Week 52 The frequency and percentage of non-responders will be provided for each week.

Data are not included for visits after histologic non-responders at Week 12 had received single-blind (to subject) APT-1011 3 mg BID in Part 2.

No statistical testing will be performed.

[figure not shown]
Author:

Version Number: 3.0

Version Date: 06NOV2019

Template No.: CS_TP_BS016 Revision 5 Reference: CS_WI_BS005

Page 47 of 70

16.4. ADDITIONAL EFFICACY

16.4.1. ADDITIONAL EFFICACY ANALYSES

All analyses of the primary and secondary efficacy variables, including the sensitivity analyses, will be repeated using the ITT population.

17. SAFETY OUTCOMES

All outputs for safety outcomes will be based on the SAF.

Safety will be presented separately for each of Part 1, Part 2 and for Parts 1 and Parts 2 combined.

- For Part 1 all subjects will be included in their double-blind dosing groups.
- For Part 2, histologic responders at Week 12 who continue into Part 2 will be included in their double-blind dosing groups.
- For Part 2, histologic non-responders at Week 12 who continue into Part 2 will be included in a single-blind APT-1011 3.0 mg BID group. Additionally, a summary will be provided for all APT-1011 3.0 mg BID during Part 2, both double-blind and single-blind.

Page 48 of 70

- For Parts 1 and 2 combined, histologic non-responders at Week 12 will be included in their double-blind dosing group (summarizing just their Part 1 safety data) and also in the single-blind APT-1011 3.0 mg BID group (summarizing just their Part 2 safety data). A summary will be provided for all APT-1011 3.0 mg BID during Part 2, both double-blind and single-blind.
- The inclusion of a group combining both double-blind and single-blind APT-1011 3.0 mg should enable a complete summary of the safety of APT-1011 3.0 mg BID in this study. And informal comparisons of original randomized dosing groups will also be possible.

There will be no statistical comparisons between dosing groups for safety data. Safety data obtained during the placebo run-in period will be listed only.

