## 4.1.6.1 Part 1: Induction (Day 1 to Week 14)

During Part 1, subjects will receive their randomized treatment for 14 weeks.

At Week 12, the subjects will undergo a response assessment, including EGD to assess endoscopic and histologic status. The process overview in Section 6.2 will be followed to determine responder status (as defined in Section 4.1.1) and inform the site thereof. Symptoms will also be assessed. The 14 days prior to Week 12 will be compared to the 14 days prior to Randomization.

Histologic responders and non-responders (at Week 12) will enter Part 2 (see Section 4.1.6.2).

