#### 4.1.6.2 Part 2: Maintenance (Week 14 to Week 52)

In Part 2, all subjects classified as histologic responders at Week 12 will continue to be treated according to the dosing group to which they were randomized for Part 1. Subjects may continue on this dose for up to 9 months after the completion of Part 1.

Subjects who are histologic non-responders (see Section 4.1.1) at Week 12 will receive single-blind 3 mg BID in Part 2.

At Week 26, subjects will undergo an EGD with biopsy, to assess histologic response. The process overview in Section 6.2 will be followed to determine responder status (as defined in Section 4.1.1) and inform the site thereof. Symptoms will also be assessed. All subjects classified as histologic responders will continue to be treated according to the dosing group to which they were randomized for Part 1 up to Week 52. The 14 days prior to Week 26 will be compared to the 14 days prior to Randomization.

Subjects who are histologic non-responders (see Section 4.1.1) at Week 26 will stop treatment at Week 28 and enter the 2-week follow-up period and exit the study.

Subjects who complete the study at Week 52 will undergo a response assessment, including EGD to assess endoscopic and histologic status. The process overview in Section 6.2 will be followed to determine responder status (as defined in Section 4.1.1) and inform the site thereof. Symptoms will also be assessed. The subject will be treated with study drug through completion of the EGD associated with the Week 52 visit. The 14 days prior to Week 52 will be compared to the 14 days prior to Randomization.

Subjects will complete a Follow-up Visit 2 weeks after the final dose of study drug (see Section 4.1.8).

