## 8.1.1 Expected Number of Subjects by Part

The following assumptions were used:

- The 1:1:1:1 (1.5 mg HS: 1.5 mg BID: 3 mg HS, 3 mg BID: placebo) randomization ratios will remain constant throughout the study.
- Based on these randomization ratios, approximately 80% of all subjects in Part 1 will be treated with an APT-1011 dosing regimen and approximately 20% of all subjects in Part 1 will be treated with placebo.
- Based upon the PR-021 study, which had slightly different histologic response criteria, it is expected that approximately 60% of patients on active treatment are expected to be a histologic responder compared to 10% on placebo. The lowest dose may be less effective.
  - Assuming a 60% histologic response rate for the 3 highest active doses of 1.5 mg BID, 3 mg HS, 3 mg BID, a 20% response rate for 1.5 mg HS, and a 10% response rate for placebo, it is expected that overall approximately 50% of active treatment will be responders at Week 12 (40 out of 80).
  - o It is expected that at Week 26 an additional 20% will drop out who were previously responders and of the PART 1 non-responders that 40% will still be non-responders.
  - After Week 26, of the remaining subjects, it is expected that approximately 20% will dropout before Week 52.

Given these assumptions, it is expected that approximately 42 patients will be responders and complete Week 26, and about 34 of those responders will complete Week 52.

The power for testing each active dose versus placebo given a histologic response rate of 60% active treatment and 10% placebo for the primary endpoint (Part 1) is equal to 97.5% (one-sided Type I error = 0.05). Additionally, the power for achieving statistical significance for all 3 of the highest active doses of 1.5 mg BID, 3 mg HS, 3 mg BID via the gatekeeping hypothesis testing approach assuming independence is approximately 0.93.

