17.1.2. TEAES LEADING TO STUDY DRUG DISCONTINUATION AND STUDY WITHDRAWAL

TEAEs leading to permanent discontinuation of study drug and sudy withdrawal will be identified as those with an answer of yes to the question 'Did the AE cause the subject to discontinue from the study?' on the Adverse Events page of the eCRF.

For TEAEs leading to discontinuation, summaries of incidence rates (frequencies and percentages) by SOC and PT will be prepared.

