17.6. OTHER SAFETY ASSESSMENTS

- The number and percentage of subjects with serum cortisol level $\leq 5 \mu g/dL$ ($\leq 138 \text{ nmol/L}$) or abnormal ACTH stimulation test (serum cortisol $\leq 16 \mu g/dL$ [$\leq 440 \text{ nmol/L}$]) will be presented
- The number and percentage of subjects discontinuing for HPA axis suppression (adrenal suppression) will be presented
- The number and percntage of subjects discontinued for hypercorticism
- The number and percentage of subjects discontinuing due to abnormal ACTH stimulation test will be presented.

Document:

Author:

Version Number: 3.0

Version Date: 06NOV2019

Template No.: CS_TP_BS016 Revision 5 Reference: CS_WI_BS005

Page 55 of 70

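### In the Parts 1 and 2 combined safety tables, the follow-up credited to a randomized group depends on its histologic response rate, so crude percentages are not comparable with placebo or 1.5 mg HS

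*SAP*

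**What the plan says.** Protocol 4.1.6.1 gives every group the same induction period: "During Part 1, subjects will receive their randomized treatment for 14 weeks". Protocol 4.1.6.2 then splits subjects by outcome. Week 12 responders stay on their randomized dose, and for the others: "Subjects who are histologic non-responders (see Section 4.1.1) at Week 12 will receive single-blind 3 mg BID in Part 2".

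SAP 17 presents safety for Part 1, for Part 2 and for both combined. In the combined presentation, "histologic non-responders at Week 12 will be included in their double-blind dosing group (summarizing just their Part 1 safety data"); their Part 2 data go to a separate single-blind 3 mg BID column. Responders contribute both parts to their randomized column. The section adds "And informal comparisons of original randomized dosing groups will also be possible" and rules out statistical comparisons of safety data.

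The planned measures carry no time at risk. SAP 17.1 gives numbers of subjects and events, and SAP 17.1.1 gives incidence by SOC and PT. For TEAEs leading to discontinuation, SAP 17.1.2 says "summaries of incidence rates (frequencies and percentages) by SOC and PT will be prepared". SAP 17.6 opens with "The number and percentage of subjects with serum cortisol level" at or below the cortisol threshold, or with an abnormal ACTH test, and names neither visit nor period. SAP 14 derives exposure in weeks for the same groupings, but no safety summary in the SAP text uses it.

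**The concern.** Leaving the randomized column is decided by Week 12 histology, which is a post-randomization outcome and the primary endpoint. A group in which most subjects respond is watched for much longer, under its own label, than one in which few respond. A percentage of subjects with an event grows with time watched, so the combined table mixes any drug effect with a difference in follow-up that the drug's efficacy creates.

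Long-term safety is a secondary objective (Protocol 3.2), and the combined table is where a reader would look for it by dose. If its percentages are set side by side, as the SAP's sentence permits, the higher doses can look less safe than placebo or 1.5 mg HS only because their subjects were followed longer.

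**Working it through.** **Inputs**
- Part 1 lasts 14 weeks (Protocol 4.1.6.1). Part 2 runs from Week 14 to Week 52, 38 weeks (Protocol 4.1.6.2).
- Response rates p (Protocol 8.1.1): 60% for 1.5 mg BID, 3 mg HS and 3 mg BID; then "a 20% response rate for 1.5 mg HS, and a 10% response rate for placebo".
- Dropout of responders (Protocol 8.1.1): 20% by Week 26, then 20% of those remaining before Week 52.
- Assumed, because the documents give no figure: an equal constant hazard h in all groups, and dropout spread evenly within each interval.

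**The plan's own figures.** Active responders: 60 × 0.6 + 20 × 0.2 = 40 of 80, as stated. Power for 60% vs 10%, 20 per group, one-sided 0.05, pooled variance: (0.5 − 1.645 × 0.1508) / 0.1285 = 1.96, giving 97.5%, as stated.

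**Mean credited follow-up, no dropout** = 14 + 38p
- Placebo: 14 + 3.8 = 17.8 weeks
- 1.5 mg HS: 14 + 7.6 = 21.6 weeks
- Each higher dose: 14 + 22.8 = 36.8 weeks
- Ratios to placebo: 36.8 / 17.8 = 2.07; 21.6 / 17.8 = 1.21

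**With planned dropout.** Mean Part 2 time of a responder = 0.20 × 6 + 0.16 × 25 + 0.64 × 38 = 29.52 weeks. Credited follow-up = 14 + 29.52p = 17.0, 19.9 and 31.7 weeks. Ratio of higher doses to placebo: 31.71 / 16.95 = 1.87 (1.86 from the rounded weeks).

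**Sensitivity of the ratio**
- Switch dated at Week 12, as the SAP derives it: 2.25 without dropout, 2.04 with.
- Everyone stops at Week 28, which Protocol 4.1 allows as the end of the study: 1.41 to 1.59, depending on switch date and dropout.
- Other response rates, no dropout: 1.64 (40% vs 10%) to 2.79 (80% vs 5%).

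**Crude percentage with no true difference** = (1 − p) × N + p × R. N = 1 − exp(−14h) is the risk of a non-responder in the randomized column. R is the risk of a responder averaged over the dropout pattern. At h = 1% per week, N = 13.06% and R = 34.70%:
- Placebo: 0.9 × 13.06 + 0.1 × 34.70 = 15.2%
- 1.5 mg HS: 0.8 × 13.06 + 0.2 × 34.70 = 17.4%
- Each higher dose: 0.4 × 13.06 + 0.6 × 34.70 = 26.0%

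| Assumed weekly hazard | Placebo | 1.5 mg HS | Each higher dose |
|---|---|---|---|
| 0.5% | 8.0% | 9.3% | 14.3% |
| 1% | 15.2% | 17.4% | 26.0% |
| 2% | 27.6% | 30.8% | 43.7% |

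**Number of tests.** Scheduled on-treatment ACTH tests fall at Weeks 12, 26 and 52 (Protocol 6.3.4). A non-responder gives the randomized column one test; a responder followed to Week 52 gives three. If, and only if, the summary counts any abnormal value over the combined period, a 5% chance abnormality per test (assumed, independent, no dropout) gives (1 − p) × 0.05 + p × (1 − 0.95³) = 5.9%, 6.9% and 10.6%. At 2% it is 2.4%, 2.8% and 4.3%; at 10%, 11.7%, 13.4% and 20.3%.

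**The case against.** **Dose gradient.** A reader might infer a false gradient across all doses. The planning rates do not support that. The three higher doses share a 60% response rate, hence the same 36.8 weeks and the same expected percentage, and 1.5 mg HS differs from placebo by only about 1.2-fold. This objection stands.

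**Phase 3 dose choice.** A reader might also infer that dose selection was distorted. The interim uses Part 1 safety (SAP 4.2), where planned follow-up is equal, and Protocol 2.5 reports that 3 mg HS was chosen after it. The combined tables were not the stated basis. This stands.

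**The sentence may be over-read.** It closes a list covering all three presentations and does not name the combined one, and formal comparisons are excluded. That is fair, but nothing restricts it to Part 1 either, so it needs qualifying.

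**Certainty.** The excess needs risk that continues after Week 14. Early-onset events would show little of it, and with 20 per group chance can hide it: at 1% per week the expected counts are 20 × 0.152 = 3.0 and 20 × 0.260 = 5.2 subjects. Not every responder reaches Week 52, because Week 26 non-responders stop at Week 28. The point is therefore one of expectation.

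**Cortisol and ACTH.** SAP 17.6 does not say that any abnormal value counts, and SAP 6.4 sets a convention for by-visit summaries. This part is an ambiguity, not an established error.

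**Visibility and direction.** Exposure is tabulated separately (SAP 14), so an alert reader could see the imbalance. The output templates are not among the documents and might show more. The bias overstates risk on active drug against placebo and so does not conceal harm from that comparison. All true, but a table that misstates the contrast still needs correcting.

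**Conclusion.** The point holds for the combined safety tables. Credited follow-up depends on response, and under the planning rates the three higher doses receive about twice that of placebo (2.07; about 1.87 with planned dropout; 1.41 to 1.59 if everyone stops at Week 28). For events that continue after Week 14, crude percentages would in expectation show an excess over placebo and 1.5 mg HS with no true difference. Its size depends on an assumed equal constant hazard, unrelated to response.

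The documents do not support going further. No spurious gradient is expected among the three higher doses, the Part 1 tables are sound on this point, and the Week 12 dose choice did not rest on the combined tables. The consequence is a misleading long-term safety comparison with placebo and 1.5 mg HS, possibly aggravated by unequal testing if SAP 17.6 means any abnormal value over the whole period.

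**What to change.** 1. Reconcile the switch date first. Protocol 4.1.6.2 starts Part 2 at Week 14. SAP 6.1 dates a switcher's first Part 2 dose to the day after the Week 12 visit, and SAP 14 correspondingly ends Part 1 dosing at that visit. Until these agree, two weeks per switcher can be credited to the wrong column.
2. In SAP 17, qualify the informal-comparisons sentence: crude percentages are compared between randomized groups for Part 1 only.
3. For the Part 2 and combined tables, add exposure-adjusted incidence beside n and %: subjects with a first event per 100 subject-weeks at risk, censored at switch or last dose.
4. In SAP 17.6, present cortisol ≤5 µg/dL and abnormal ACTH by visit, with the number tested as denominator.

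The cost is SAP wording, longer tables and a time-to-first-event derivation that SAP 14 does not now contain. Conduct and the primary analysis are untouched.

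The adjusted rate has its own weakness: it assumes a roughly constant hazard. Suppose an identical 20% risk in every group fell wholly within Part 1, at Week 7 on average and unrelated to response. Placebo would show 100 × 0.20 / (0.2 × 7 + 0.8 × 17.8) = 1.28 per 100 weeks, and a higher dose 100 × 0.20 / (0.2 × 7 + 0.8 × 36.8) = 0.65, a false protective effect. The adjusted rates must therefore be read with the Part 1 table, and the SAP should say so.
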